4.3 PROHIBITIONS AND RESTRICTIONS

The parent/guardian must be willing and able to adhere to the following prohibitions and restrictions during the course of the study for their child to be eligible for participation:

1. In case of a new Ebola outbreak: participants and their parent/guardian must not travel to an area with an Ebola outbreak while the participant is enrolled in the study from the start of screening onwards until the last study visit. If applicable, any travelling to an area with an Ebola outbreak should be documented in the case report form (CRF). The date of travel and the destination should be clearly identified.
2. Ensure that their child does not receive any experimental medication (including experimental vaccines other than the study intervention) as described in Section 7.

5 INTERVENTION ALLOCATION AND BLINDING

5.1 BLINDING

As this is an open-label study, blinding procedures are not applicable.

6 DOSAGE AND ADMINISTRATION

All participants will receive the Ad26.ZEBOV vaccine, at a concentration of 5×10^{10} vp, as a 0.5 millilitres (mL) IM injection into the deltoid muscle.

Study intervention will be prepared by a pharmacist or qualified staff member with primary responsibility for study intervention preparation and dispensing of the vaccine.

Ad26.ZEBOV will be administered as a 0.5 mL IM injections in the deltoid muscle, by a study intervention administrator. The injection site should be free from any injury, local skin conditions, or other issue that might interfere with the evaluation of local reactions. No local or topical anaesthetic will be used prior to the injection.

Participants will remain at the site for at least 30 minutes after the vaccination for the detection of any acute reactions, or longer if deemed necessary by the investigator (e.g. in case of a grade 3 AEs). As with any vaccine, allergic reactions following vaccination with the study intervention are possible. Therefore, appropriate drugs and medical equipment to treat acute anaphylactic reactions must be immediately available, and a medically qualified member of study-site personnel trained to recognize and treat

anaphylaxis must be present in the clinic during the entire vaccination procedure and post-vaccination monitoring period.

The investigator must provide emergency care as needed for any participant who experiences a life-threatening event. The site will have facilities, equipment and the ability to manage an anaphylactic reaction. If additional therapy is required, the investigator will arrange for transport to the closest appropriate facility for continuing care.

The Site Investigational Product Procedure Manual specifies the procedures for administration of the study intervention.

Ad26.ZEBOV will be manufactured by Janssen Vaccines & Prevention B.V. and provided under the responsibility of the sponsor, LSHTM. Please refer to the IB for a list of excipients.

6.1 CRITERIA FOR POSTPONEMENT OF VACCINATION

A participant will not be given any vaccination if he/she experiences any of the following events at the scheduled time for vaccination:

- An acute illness at the time of vaccination (this does not include minor illnesses such as diarrhoea or mild upper respiratory tract infection).
- An axillary temperature $\geq 38^{\circ}\text{C}$ at the time of vaccination.

Participants experiencing any of these events may be rescheduled for vaccination at a later time point within the window allowed for screening, or be withdrawn from vaccination at the discretion of the investigator and after consultation with the sponsor.

7 CONCOMITANT THERAPY

Concomitant therapies that the participant is taking at the time of screening must be recorded in the CRF at screening.

Should immunisation with an inactivated vaccine be required, it should be administered at least 15 days before or after administration of the study intervention in order to avoid any potential interference in efficacy of the routine immunizations or the interpretation of immune responses to study intervention, as well as to avoid potential confusion with regard to attribution of adverse reactions. However, if a vaccine is indicated in a post-exposure setting (e.g., rabies or tetanus), it must take priority over the study intervention. A participant will not postpone, forego, or delay the receipt of any recommended vaccine according to local schedules (e.g. EPI schedule according to the WHO regional office for West Africa).

Analgesic/antipyretic medications and non-steroidal anti-inflammatory drugs may be used post-vaccination in case of medical need (e.g., fever or pain). Use of these medications as routine prophylaxis prior to study intervention administration is not recommended. The use of these medications must be documented.

Concomitant therapies must be recorded from screening onwards until 28 days post-vaccination.

Use of any experimental medication (including experimental vaccines other than the study intervention) during the study is not allowed.

The sponsor must be notified in advance (or as soon as possible thereafter) of any instances in which prohibited therapies are administered.

8 STUDY EVALUATIONS

Prior to any study-related activities being performed, participants, or participant's parent/guardian, must have signed a study ICF (see Section 15.2.3 Consent)

8.1 STUDY PROCEDURES

8.1.1 Overview

The TIME AND EVENTS SCHEDULE summarises the frequency and timing of all study procedures, which are provided in the following sections. Additional unscheduled study visits may be required if, in the investigator's opinion, further clinical or laboratory evaluation is needed.

Visit Windows

Visit windows are provided in the TIME AND EVENTS SCHEDULE. If a participant did not receive the study intervention on the planned day of vaccination, the timings of the next visits post-vaccination will be determined relative to the actual day of vaccination. The participant should be encouraged to come within these required windows.

Blood Sampling Volume

The approximate blood volumes collected in this study are indicated in the TIME AND EVENTS SCHEDULE. These study-related blood volumes obtained at each study visit (including any losses during phlebotomy) will not exceed 3% of the total blood volume. The total volume of blood is estimated at 80 to 90 mL/kg body weight; 3% is 2.4 mL blood per kg body weight. [10] The allowable blood volume calculations are based on the 3rd percentile for growth charts for 1 to 5-year-old [11] and 6- to 10-year-old children. [12]

Repeat or unscheduled samples may be taken for safety reasons or for technical issues with the samples.

8.1.2 Screening Period

After signing and dating the ICF (see Section 16.2.3) and up to 28 days before Day 1 (day of vaccination), screening assessments will be performed as indicated in the TIME AND EVENTS SCHEDULE. Screening may be split into multiple days or visits.

Only participants complying with the criteria specified in Section 4 will be included in the study. The investigator will provide detailed information on the study to the participant and his/her parent/guardian will obtain written informed consent prior to study participation of the child.

After reading but before signing the ICF, the TOU will be administered to the parent/guardian. If the parent/guardian fails the TOU, they may repeat the test twice (and have to pass the third time for their child to be eligible) (for details, see Section 15.1).

The overall eligibility of the child to participate in the study will be assessed once all the screening results are available. Retesting of values (i.e. haematology) that lead to exclusion is allowed once using an unscheduled visit. If rescreening is required, all screening procedures (except TOU) should be repeated. Rescreening is allowed one time at the discretion of the study doctor. Study participants who qualify for inclusion will be contacted and scheduled for vaccination within 28 days.

A serum sample will be taken before vaccination at D1, to serve as a pre-vaccination baseline sample for immunogenicity assessments (see Section 8.4).

8.1.3 Vaccination Period

If eligible, the participant will be invited to come for the vaccination visit (Day 1). The investigator should ensure that all eligibility criteria have been met during the screening period. If a participant's clinical status changes (including available laboratory results or receipt of additional medical records) after screening but before the vaccination (Day 1) such that he/she no longer meets all eligibility criteria, then the participant should not be enrolled. Retesting of values and rescreening might be considered (see Section 8.1.2 for further information). Rescheduling of the vaccination (Day 1) visit, if the participant has an acute illness, is allowed within the screening window.

Before vaccination, a brief physical examination and measurement of vital signs will be performed.

Participants will be vaccinated as described in Section 6. After vaccination, participants will remain under observation at the study site for at least 30 minutes for surveillance for any acute reactions, or longer if deemed necessary by the investigator. Following the vaccination, any unsolicited, solicited local or systemic AEs, and vital signs will be documented by study-site personnel at the end of this observation period.

Upon discharge from the site, the parent/guardian will be provided with a thermometer (to measure body temperature), a ruler (to measure local injection site reactions), and a participant diary to record body temperature and solicited local (at the injection site) and systemic symptoms and will be trained on how to collect this information. Symptoms of solicited local and systemic AEs will be collected in the diary in the evening after the vaccination and then daily for the next 7 days at approximately the same time each day. Diaries will be completed at home by either a project field worker who will visit the participant during daily visits or by the parent/guardian and checked by a project field worker. The investigator or clinical designee will review information from the participant's diary.

Participants will come to the site 7 days after the vaccination (Day 8) as indicated in the TIME AND EVENTS SCHEDULE. The participant's diary will be reviewed by study-site personnel. The investigator will examine the injection site for occurrences of erythema, swelling, or tenderness at these visits in order to complete the relevant parts of the CRF.

Unsolicited AEs will be reported from the first day of vaccination until 28 days post-vaccination (Day 29).

SAEs and/or special reporting situations that are related to study procedures will be reported from the time a signed and dated ICF is obtained onwards until the end of the study (Day 29). All other SAEs and/or special reporting situations will be reported from the day of vaccination onwards until the end of the study (Day 29).

Participants will come to the site 7 and 21 days after the vaccination (Day 8 and Day 22) for safety and immunogenicity assessments. Please refer to 8.4 for details on the immunogenicity evaluations.

The parent/guardian will be instructed to contact the investigator anytime during the course of the study if their child experiences any AE or intercurrent illness that they perceive as relevant and/or can be possibly related to study intervention in their opinion.

When an enrolled participant completes or withdraws from the study, the investigator will complete an end-of-study form for the individual participant and provide a specific date for the end-of-study observation(s). When a participant withdraws before completing the study, the reason for withdrawal (if available) will be documented in the CRF and in the source documents.

Participants who appear to be lost to follow-up will be contacted, as per local practice, and the data recorded in the CRF. Participants lost to follow-up will have all data included for analysis.

8.2 PROCEDURES IN CASE OF A STUDY PAUSE

A study pause can affect participants that are awaiting the booster vaccination. After approval is granted to restart the study, participants who are awaiting the booster vaccination and whose screening period is longer than the protocol-defined 28 days as a result of a study pause, will be allowed to rescreen once (following the screening procedures described in Section 8.1.2, excluding TOU). Participants that are rescreened due to a pause must have new safety assessments (including full blood count, physical examination, and vital signs) within 28 days of the booster vaccination. The TOU does not need to be repeated. After screening, these participants will follow the same study procedures as those participants who were unaffected by a study pause (described in Section 8.1.3).

8.3 SAFETY EVALUATIONS

8.3.1 Safety Assessments

The Principal Investigator, together with the Chief Investigator and the sponsor's medical safety officer or delegate, will be responsible for the safety monitoring of the study, and will halt vaccination of further participants in case any of the pre-specified pausing rules described in Section 8.3.2 have been met. Further safety measures with regards to vaccination are described in Section 6.1.

An independent medical reviewer will be appointed by the sponsor before the start of the study to perform review of the safety data during the study. Details regarding this role are provided in Section 10.7.

Symptoms of solicited local and systemic AEs will be collected in the diary in the evening after the vaccination and then daily for the next 7 days. Unsolicited AEs will be collected from vaccination until 28 days post-vaccination (Day 29). Serious adverse events and/or special reporting situations that are related to study

procedures will be reported from the time a signed and dated ICF is obtained onwards until the end of the study (Day 29). All other SAEs and/or special reporting situations will be reported from the day of vaccination onwards until 28 days post-vaccination.

Any clinically relevant changes must be recorded on the AE section of the CRF.

Any clinically significant abnormalities persisting at the end of the study/early withdrawal will be followed by the investigator until resolution or until a clinically stable condition is reached.

All AEs will be coded for severity according to the criteria presented in Section 11.1.3.

The study will include the following evaluations of safety and reactogenicity according to the time points provided in the Time and Events Schedule:

Adverse Events

Adverse events will be reported as specified in Section 11.3.1.

Solicited Adverse Events

After vaccination, participants will remain under observation at the study site for at least 30 minutes for surveillance for any acute reactions, or longer if deemed necessary by the investigator. Symptoms of solicited local and systemic AEs will be collected in the diary in the evening after the vaccination and then daily for the next 7 days. Diaries will be completed at home by either a project field worker who will visit the participant during daily visits or by the parent/guardian and checked by a project field worker for 6 days. Day 8 of the diary will be completed by study site staff at the clinic. Diary information will be transcribed by the study personnel in the diary CRF pages. Once a solicited symptom from a diary is considered to be of severity Grade 1 or above, it will be referred to as a solicited AE.

Solicited Injection Site (Local) Adverse Events

Parents/guardians (or the project field worker) will be asked to note in the diary occurrences of tenderness, erythema and swelling at the study intervention injection site daily for 6 days post-vaccination (day of vaccination and the subsequent 6 days). The extent (largest diameter) of any erythema and swelling should be measured (using the ruler supplied) and recorded daily. Day 8 of the diary will be completed by study staff at the site clinic.

- Injection Site Tenderness**

Injection site tenderness is a painful sensation localized at the injection site upon palpation or movement of the limb. Due to the subjective nature of the reaction, the severity assessment of tenderness is self-reported (if a participant is unable to provide self-report, other reporters include parent/care giver or health care provider).

- Injection Site Erythema**

Injection site erythema is a redness of the skin caused by dilatation and congestion of the capillaries localized at the injection site. It can best be described by looking and measuring.

- Injection Site Swelling**

Injection site swelling is a visible enlargement of the site of injection. It may be either soft (typically) or firm (less typical).

Note: Any other injection site events not meeting the above case definitions should be reported separately as unsolicited AEs.

Solicited Systemic Adverse Events

Parents/guardians will be instructed on how to record daily temperature using a thermometer provided for home use. The axillary temperature of the participant should be recorded in the diary in the evening of the day of vaccination, and then daily for the next 6 days at approximately the same time each day. The participant's temperature on Day 8 will be taken by study staff at the site clinic. If more than one measurement is made on any given day, the highest temperature of that day will be used in the CRF.

In this protocol, fever is defined as an endogenous elevation of body temperature $\geq 38^{\circ}\text{C}$, as recorded in at least one measurement.

Parents/guardians will also be instructed on how to note daily in the diary symptoms for 6 days post-vaccination (day of vaccination and the subsequent 6 days) any of the following events:

- body temperature
- fatigue/malaise
- chills
- headache
- nausea/vomiting
- muscle pain
- joint pain
- loss of appetite, in young children

Symptoms 7 days post vaccination (Day 8) will be assessed and recorded by study staff at the site clinic.

Physical Examination

A full physical examination will be performed at the screening visit. At subsequent study visits a brief, symptom-directed examination will be performed based on any clinically relevant issues, clinically relevant symptoms and medical history. The symptom-directed physical examination may be repeated if deemed necessary by the investigator. Physical examinations will be performed by the investigator or by a designated medically-trained clinician. Physical examination findings (i.e. abnormalities) prior to vaccination (Day 1) are to be recorded as medical history, but after vaccination as an AE.

Vital Signs

Axillary temperature, blood pressure, pulse/heart rate (beats per minute), and respiratory rate (breaths per minute) will be assessed.

Blood pressure and pulse/heart rate measurements will be assessed with a completely automated device. Manual techniques will be used only if an automated device is not available. Pulse/heart rate measurements should be preceded by at least 5 minutes of rest in a quiet setting without distractions.

Clinical Laboratory Tests

A haematological assessment (i.e., full blood count) will be performed by the local laboratory at the time points indicated in the TIME AND EVENTS SCHEDULE. The investigator must review the laboratory report, document this review, and record any clinically relevant changes on the AE page and/or the screening page of the CRF. Laboratory reports must be filed with the source documents.

A full blood count will include:

- haemoglobin
- haematocrit
- red blood cell (RBC) count
- white blood cell (WBC) count with differential
- platelet count

Note: a WBC evaluation may include any abnormal cells, which will then be reported by the laboratory. An RBC evaluation may include abnormalities in the RBC count, or RBC morphology, which will then be reported by the laboratory.

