4.2 EXCLUSION CRITERIA

Any potential participant who meets any of the following criteria will be excluded from participating in the study:

1. Participants in the EBOVAC-Salone trial who were allocated to the control arm receiving the WHO-prequalified Meningococcal Group A, C, W135 and Y conjugate vaccine.
2. Participants in the EBOVAC-Salone trial who were age 12 years and older at the time of dose 1 vaccination.
3. Known allergy or history of anaphylaxis or other serious adverse reactions to vaccines or vaccine products (including any of the constituents of the study vaccine, e.g., polysorbate 80, ethylenediaminetetraacetic acid or L-histidine for Ad26.ZEBOV vaccine), including known allergy to chicken or egg proteins and aminoglycosides (gentamicin).
4. Presence of acute illness (this does not include minor illnesses such as mild diarrhoea or mild upper respiratory tract infection) or axillary temperature $\geq 38^\circ\text{C}$ on Day 1. Participants with such symptoms will be excluded from enrolment at that time but may be rescheduled for enrolment at a later date within the screening window.
5. Clinically significant history of skin disorder (e.g., psoriasis, contact dermatitis), allergy, symptomatic immunodeficiency, cardiovascular disease, respiratory disease, endocrine disorder, liver disease, renal disease, gastrointestinal disease, neurological illness as judged by the investigator or other delegated individual.
6. Adolescent girls who are known to be pregnant or breastfeeding at screening.

7. Received a blood transfusion or other blood products within 8 weeks of vaccination day.
8. Children who have been vaccinated with live-attenuated vaccines within 30 days before the study vaccination, and with inactivated vaccine within 15 days before the study vaccination.
9. Children who, in the opinion of the investigator, are unlikely to adhere to the requirements of the study or are unlikely to complete the vaccination and observation
10. Any other finding which in the opinion of the investigator or other delegated individual would increase the risk of an adverse outcome from participation in the study, e.g. history of thrombotic thrombocytopenia syndrome (TTS) or heparin-induced thrombocytopenia and thrombosis (HITT).

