10.2 SAMPLE SIZE DETERMINATION

Approximately 50 participants are expected to be enrolled into this trial (approximately 25 for each age group). The sample size is a convenience sample and is not based on formal hypothesis testing considerations.

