11.1 DEFINITIONS

11.1.1 Adverse Event Definitions and Classifications

Adverse Event

An AE is any untoward medical occurrence in a clinical study subject administered a medicinal (investigational or non-investigational) product. An AE does not necessarily have a causal relationship with the treatment. An AE can therefore be any unfavourable and unintended sign (including an abnormal finding), symptom, or disease temporally associated with the use of a medicinal (investigational or non-investigational) product, whether or not related to that medicinal (investigational or non-investigational) product. (Definition per International Council for Harmonisation of Technical Requirements for Pharmaceuticals for Human Use [ICH].)

This includes any occurrence that is new in onset or aggravated in severity or frequency from the baseline condition, or abnormal results of diagnostic procedures, including laboratory test abnormalities.

Note: For the time period of AE collection, see Section 11.3.

Serious Adverse Event

A SAE, based on ICH and EU Guidelines on Pharmacovigilance for Medicinal Products for Human Use, is any untoward medical occurrence that at any dose:

- Results in death
- Is life-threatening (the participant was at risk of death at the time of the event. It does not refer to an event that hypothetically might have caused death if it were more severe.)
- Requires inpatient hospitalisation or prolongation of existing hospitalisation
- Results in persistent or significant disability/incapacity
- Is a congenital anomaly/birth defect
- Is a suspected transmission of any infectious agent via a medicinal product
- Is medically important*

*Medical and scientific judgment should be exercised in deciding whether expedited reporting is also appropriate in other situations (other than those listed above), such as important medical events that may not be immediately life-threatening or result in death or hospitalization but may jeopardize the participant or may require intervention to prevent one of the other outcomes listed in the definition above. These should usually be considered serious.

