6. SAFETY

No formal statistical testing of safety data is planned. Safety data analysis will be performed on the full analysis set.

Safety data will be analysed descriptively (including 95% CI, if applicable). Baseline for all safety parameters will be defined as the last value before the booster dose.

The safety and tolerability data will include the following:

Solicited local and systemic adverse events (reactogenicity) until 7 days post vaccination.

Unsolicited adverse events, from provision of informed consent onwards until 28 days after booster vaccination.

Serious adverse events (SAEs) until the end of the study (Day 29).

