1. PERIODIC ALLOCATION OF ADVERSE EVENTS

Solicited AEs are always allocated to the Post boost vaccination period. Unsolicited AEs are allocated to the different periods according to the following rules:

Step 1: Allocation of events to the periods:

Adverse events present in the SDTM database are allocated to periods based on their start date/time. If the start date/time of an event falls between (or on) the start and stop date/time of a period, the AE is attributed to that period (treatment-emergent principle).

Incomplete dates (i.e. time and/or day and/or month and/or year missing):

- In case of partial start or stop dates, the events are allocated to the periods using the available partial information on start and end date; no imputation will be done. If, for instance, for the AE start date only month and year are available, these data are compared to the month and year information of the periods. This rule may lead to multiplication of the event because of its assignment to multiple periods (see below example).

- In case of a completely missing end date (i.e., only for the calculation of duration):

- o In case the AE is not flagged as ongoing, the end date is considered as unknown, therefore the date will remain missing
- o In case the AE is flagged as ongoing the date is imputed by the cut-off date of the analysis for participants still ongoing in the study, and by the end date of the last period for participants who discontinued or completed the trial.

Examples:

Screening period: start date: 14JUN2021 - stop date: 28JUN2021

Post-boost vaccination period: start date: 28JUN2021 - stop date: 19JUL2021

- 1) Adverse event: start date: JUN2021- stop date: 15JUL2021

As the start date only has information about month and year, only this information will be used from the periods (i.e. assuming any day of Jun is possible) and therefore the AE will be assigned to the Screening Period as well as to the Post-boost vaccination Period.

- 2) Adverse event: start date: JUL2021- stop date 14JUL2021

As the AE starts after the Screening Period and after the start of the Post-boost vaccination period, it is only assigned to the Post-boost vaccination period.

Remarks:

- In addition to the date information, time information is considered to allocate AEs to periods, if available.

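### Non-fever solicited systemic symptoms get no graded pre-dose record, so a symptom already present at the booster is tabulated as post-booster reactogenicity

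*Protocol*

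**What the plan says.** - **Counting rule.** Protocol section 8.3.1 sets the threshold for a solicited AE: "Once a solicited symptom from a diary is considered to be of severity Grade 1 or above". The child's state before the dose plays no part.
- **Period.** SAP Attachment 1: "Solicited AEs are always allocated to the Post boost vaccination period". A remark in the same attachment rules out the screening period for these events.
- **When symptoms are recorded.** The Time and Events Schedule with its footnotes, and protocol sections 3.1 and 8.1.3, start solicited recording during the 30-minute observation after injection. The diary takes over that evening. SAP Attachment 3 builds the solicited dataset from the diary and from on-site assessments made after the dose.
- **What happens before the dose on Day 1.** Section 8.1.3 schedules a short examination and vital signs, which include axillary temperature. Under section 8.3.1, abnormal findings before vaccination become medical history, which SAP section 4.4 only lists. The Schedule places history-taking at screening, up to 28 days earlier.
- **Who may be boosted.** Exclusion criterion 4 bars acute illness on Day 1, but "this does not include minor illnesses such as mild diarrhoea or mild upper respiratory tract infection". Section 6.1 makes a similar allowance for postponement. Both act on a temperature of 38 °C or above.
- **Relatedness.** SAP section 6.1.1 treats all solicited AEs as related. Protocol section 11.1.2 and SAP section 6.1.2 say this only of local ones.
- **Item list.** The protocol's diary list includes chills and, in young children, loss of appetite. SAP section 6.1.1.2 omits both.

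**The concern.** Safety and tolerability is the first primary objective, and there is no control group. The child's own state just before the injection is the only internal reference for systemic reactogenicity. The minor illnesses that do not bar vaccination can themselves cause headache, malaise, nausea or vomiting, aches and poor appetite, which are the symptoms the diary asks about.

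Elsewhere the plan does separate what was there before from what came after. A laboratory abnormality is emerging only if it is worse than baseline (SAP section 6.2), and unsolicited AEs are assigned to periods by start date (SAP Attachment 1). Solicited symptoms get neither treatment. The rate, time to onset and duration of systemic events could all absorb illness that preceded the dose. If the pre-dose grade is not collected on the day, it cannot be recovered later.

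**Working it through.** **Step 1: follow one child through the rules.** Suppose a Grade 1 headache starts the day before the booster, with a mild cold and a temperature below 38 °C.

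1. Exclusion criterion 4 and section 6.1 do not stop vaccination.
2. Before the dose the child has an examination and vital signs. The headache is not graded, and it may or may not reach medical history.
3. That evening the diary shows headache Grade 1, so section 8.3.1 makes it a solicited AE.
4. SAP Attachment 1 puts it in the post-booster period.
5. SAP Attachment 3 derives the start date from the diary day, so the start is Day 1. With SAP section 6.1.3, time to onset = first-onset date − reference date + 1 = 1, taking the vaccination day as reference.
6. SAP section 6.1.1 labels it related.
7. The child enters the number and percentage with at least one event.

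**Step 2: which items are exposed.** The protocol lists eight systemic items. Body temperature has a pre-dose value, which leaves 8 − 1 = 7 without one. The SAP lists six including fever, which leaves five.

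**Step 3: scale.** The plan states no figure on this point to reproduce. Inputs:

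- n = 25 per age group (protocol section 10.2, approximate; "The sample size is a convenience sample and is not based on formal hypothesis testing considerations");
- exact Clopper-Pearson intervals (SAP section 2);
- b, the share of children with a solicited-type symptom before the dose, and r, the vaccine-induced rate. The documents give neither, so both are assumptions.

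One child is 1/25 = 4 points. Exact 95% intervals: 0/25 = 0% (0 to 13.7), 1/25 = 4% (0.1 to 20.4), 2/25 = 8% (1.0 to 26.0).

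Chance of at least one such child in a group = 1 − (1 − b)^25. For b = 5% this is 72%; for b = 20% it is 99.6%.

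If the two sources are independent and every pre-dose symptom lasts until the first post-dose record, the observed rate is 1 − (1 − r)(1 − b) and the excess over r is b(1 − r):

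| r (assumed) | b (assumed) | Observed rate | Excess, points | Children per 25 |
|---|---|---|---|---|
| 10% | 5% | 14.5% | 4.5 | 1.1 |
| 10% | 20% | 28.0% | 18 | 4.5 |
| 40% | 5% | 43.0% | 3 | 0.75 |
| 40% | 20% | 52.0% | 12 | 3 |

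The excess shrinks as r rises, because more of the affected children would have had a systemic event anyway.

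**The case against.** - **The AE definition.** A reader might infer that the diary rule contradicts protocol section 11.1.1, which mentions "any occurrence that is new in onset or aggravated in severity or frequency from the baseline condition". It does not. The definition covers any untoward occurrence after a product is given, and this phrase is introduced as something the term includes. It does not restrict the term.
- **The SAP baseline.** SAP section 6 says "Baseline for all safety parameters will be defined as the last value before the booster dose", and a reader might take that as a promised baseline for diary symptoms. The SAP applies baselines to laboratory values and vital signs, and no rule extends this to the diary. The gap is a missing measurement, not a breached commitment.
- **Partial capture.** The Day 1 examination is symptom-directed, eligibility is rechecked, and concomitant therapies are recorded from screening, with special attention to analgesics and antipyretics. This stands in part: some affected children could be identified. But the information is ungraded, medical history is only listed, and nothing links it to the solicited tables.
- **Causality.** Under the protocol an investigator may judge a systemic symptom unrelated, and the SAP's own headache example carries a doubtful attribution. This also stands in part. SAP section 6.1.1 conflicts with it, and relatedness does not remove an event from the all-events rate.
- **Consequences.** Counting every post-dose symptom is a conservative and defensible convention. The study is descriptive, the pausing rules do not turn on mild symptoms, and severity tables let Grade 3 events be read separately. All of this stands. It makes the point an improvement worth making, not an error that invalidates the analysis.

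**Conclusion.** The point holds for the non-fever systemic symptoms. The plan has no structured, graded pre-dose record of them and no rule that would use one, so a symptom present before the injection and still present that evening is reported as post-booster reactogenicity starting on Day 1. It does not extend to fever. Chills and loss of appetite are exposed in the protocol's diary, but the SAP's systemic list would not analyse them as it stands.

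The size cannot be derived from the documents. The ranges of 4.5 to 18 points (r = 10%) and 3 to 12 points (r = 40%) rest on an unsourced b of 5% to 20%, on independence and on persistence of the symptom. They show scale only. A reader might infer that a pre-dose prevalence of 5% to 20% adds the same number of points to the rate. That ignores overlap with children who would have had a systemic event regardless. Any inflation is likely to be mainly low-grade, since only minor illness is admitted. No sample size, power or test is affected.

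**What to change.** 1. **Collect.** In the Day 1 column of the Time and Events Schedule and in protocol section 8.1.3, add a grading of the same systemic list, on the diary or CRF form, just before the injection.
2. **Report.** In SAP section 6.1.3, keep the planned all-events rate. Beside it show the pre-dose row and the rate of symptoms that are new or of higher grade than before the dose.
3. **Reconcile.** Bring SAP section 6.1.1 into line with protocol section 11.1.2 and SAP section 6.1.2 on relatedness of systemic solicited AEs, and SAP section 6.1.1.2 into line with the item list in protocol section 8.3.1.

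The cost is one form column at a visit where staff already examine the child, a few minutes per child, and two rates to present instead of one. Eligibility, dosing and clinical procedures stay as they are. The grading has to be in place before children are boosted.
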